Motivated by the success of dopaminergic drugs in treating rigidity associated with Parkinson's disease, some neurologists have used carbidopa-levodopa to attempt to improve spasticity in ALS and PLS patients. However, data on the efficacy of carbidopa/levodopa is limited. In unpublished data at this institution (Table 1) carbidopa-levodopa reduced spasticity and improved function in about half of the ALS and PLS patients that received the drug. Given the limited data and potential to improve the quality of life of these patients, the effectiveness of carbidopa-levodopa in ALS and PLS patients with severe spasticity should be studied. Our hypothesis is that administration of carbidopa-levodopa will improve spasticity in ALS and PLS patients.

Objectives

1. Determine the effect of carbidopa-levodopa on spasticity in ALS and PLS patients by a patient reported outcome measure.
2. Determine the effect of carbidopa-levodopa on objective motor function in patients with ALS and PLS.

Significance

ALS and PLS are neurodegenerative diseases of the motor tract that markedly reduce patients' function. In addition to the lack of curative therapies, there is a lack of symptomatic treatments. Spasticity is a key symptom of ALS and PLS that causes pain and limits patient function. The potential for carbidopa-levodopa to improve spasticity in these patients is intriguing. If carbidopa/levodopa is effective in reducing spasticity in these patients, they could have improvement in their functional status.

Research Plan

Design: This study is an interventional, placebo-controlled, single site, double-blind randomized crossover clinical trial. Identified participants will be randomized to receive either placebo or carbidopa-levodopa for a period of three weeks before crossing over to the other arm of the study. The two periods will be separated by a one day washout period. Below is a schematic showing examples of the randomized treatment periods. Where A represents a 3 week treatment period with carbidopa-levodopa and B represents a 3 week treatment period with placebo.

Participant 1: A->washout day->B

Participant 2: B->washout day->A

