Participant Schedule Summary: Participation in this study will last for 6 weeks from the initial study visit. At the initial study visit, the participant's vital signs will be taken and the participant will undergo a neurological exam. Following this, the participant will complete the outcome measures as described above. The participant will leave with three weeks of the assigned study medication or placebo. At the end of each week, the participant will complete the spasticity, pain, and spasm numerical rating scales at home. At the end of the third week, the participant will return for a research visit where the exam and outcome measures will be repeated. The participant will cross over to the other treatment arm, and the above process will be repeated. After the second three week period, the participant will come in for a final assessment. At that point the participant's role in the study will be concluded. At each visit, potential side effects will be discussed. Over the course of the study, participants will be called by phone one week after the first visit and one week after the second visit to assess for side effects

Statistical analysis: The primary outcome data will be assessed for normality. If the data is normally distributed, analysis will be performed using ANOVA to compare the baseline and two treatment groups. Further testing for differences between groups will be carried out using the Paired-samples T-test. If the data is not normal, the non-parametric Kruskal-Wallis one way analysis of variance followed by the

Mann-Whitney U test will be used. As to the secondary variables, the data from the pain and spasm numerical rating scales will be analyzed like the spasticity data described above. The time data collected by the TUG, 10 meter walk, and 9 Hole Peg Tests will be analyzed via ANOVA, with further testing between groups performed by the Paired-samples T-test. The Ashworth scale and MRC will be compared between groups using Kruskal-Wallis one way analysis of variance followed by the Mann-Whitney U test as indicated. These non-parametric tests will be used as the Ashworth and MRC data will likely not be normally distributed.

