As for sample size, given the preliminary data, we expect the intervention to have a moderate to moderate-high effect. Thus with $\alpha=0.05$, power=0.07, and expected effect size of 0.7, the required sample size is 15 participants. This number is total given this is a paired analysis with the patients serving as controls for themselves.

Data Management:

Each participant will be given a coded ID number, and the spreadsheet containing the code correlating the patient's name with their study number will be kept on an encrypted, password-protected document (known only by members of the research team), which is behind the Washington University Department of Neurology firewall (accessible only by those with a department of Neurology account). Data collected during this study will be stored in RedCap.

Potential Benefits: In a case series of patients with ALS or PLS who have received carbidopa-levodopa at the Washington University School of Medicine Neuromuscle clinic, about one half have reported improvement in their symptoms of spasticity. These improvements have ranged from feeling less tightness, to improved gait and manual dexterity. Given the limitations of this data and the apparent ineffectiveness in some patients, no benefit is certain. Participants will be provided with a \$50 gift card for their time and effort. Parking validation will also be provided for study visits.

Potential Risks: The side effects most commonly associated with carbidopa-levodopa are diarrhea, orthostatic hypotension, and somnolence. Other rare adverse effects include hallucinations and dyskinesias. The dose of carbidopa-levodopa to be used in this study is commonly used in the Parkinson's disease patient population and is well tolerated. Additionally, the titration from the equivalent of one half of a 25/100mg tab to the equivalent of a full tab over a week should reduce the incidence of side effects.

Adverse Events: Participants in this study will be informed of the possible adverse effects of the medication and instructed to call the study coordinator if they begin to exhibit any of these symptoms. In particular, at each study visit and during the phone calls after the first and second study visits, the participants will be asked about symptoms of suicidal ideation, dyskinesia, and neuroleptic malignant syndrome among other possible side effects..All adverse events will be reviewed monthly by the study PI.

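### The rank tests planned for this crossover (Kruskal-Wallis, Mann-Whitney) are for independent groups; they discard the pairing that N=15 depends on and can cost much of the power

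*Combined protocol and SAP*

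**What the plan says.** The Design paragraph describes a two-period crossover in which participants "receive either placebo or carbidopa-levodopa for a period of three weeks before crossing over to the other arm of the study". Each person therefore supplies a baseline, a drug and a placebo value.

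The Statistical analysis section branches on normality for the primary spasticity scale, and the pain and spasm scales follow the same rule:

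- If normal: "ANOVA to compare the baseline and two treatment groups", and then "Further testing for differences between groups will be carried out using the Paired-samples T-test".
- If not normal: "If the data is not normal, the non-parametric Kruskal-Wallis one way analysis of variance", followed by the Mann-Whitney U test.

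For the examiner-rated scales there is no branch: "The Ashworth scale and MRC will be compared between groups using Kruskal-Wallis one way analysis of variance followed by the Mann-Whitney U test". That sentence closes by limiting the Mann-Whitney step to where it is indicated; the Kruskal-Wallis step carries no condition.

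The sample-size paragraph gives "power=0.07, and expected effect size of 0.7, the required sample size is 15 participants" and adds: "This number is total given this is a paired analysis with the patients serving as controls for themselves".

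**The concern.** Kruskal-Wallis and Mann-Whitney take their null distribution from independent groups. Here the groups are the same 15 people measured under different conditions. The non-normal branch therefore contradicts both the paired t-test in the normal branch and the paired basis of the sample size.

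Mann-Whitney does have a valid use in a two-period crossover: comparing within-person period differences between the two sequence groups. That is not what is written. The section compares baseline, drug and placebo, and never mentions sequences or period differences. Neither the signed-rank nor the Friedman test appears anywhere.

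If a person's scores are positively correlated, an independent-groups test overstates the error of the drug-placebo comparison. A real effect may be missed, in a trial of 15 with little power to spare.

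**Working it through.** **Inputs from the documents.** Alpha 0.05 (sidedness not stated), effect size 0.7 (type not stated), N=15, power printed as 0.07.

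**Assumptions.** The effect size is read as mean difference divided by the SD of the within-person difference, because the text calls the analysis paired. Testing is two-sided at 5%, with one value per person per condition (the plan does not say which weekly score is used). The within-person correlation ρ is not given, so it is varied from 0 to 0.8.

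**1. Reproduce N=15.** For a paired t-test, power comes from the noncentral t with n−1 df and noncentrality 0.7√n. At n=15 this is 0.7 × 3.873 = 2.71 on 14 df, giving two-sided power 0.71. Solving for n:

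- two-sided, power 0.70: 14.6, so 15
- one-sided, power 0.80: 14.1, so 15
- power 0.07 as printed: 2

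So 15 is a paired-test figure, and the printed power looks like a slip, most simply for 0.70. That is a separate matter.

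**2. Why correlation matters.** The SD of a within-person difference is σ√(2(1−ρ)); an independent-groups test behaves as if it were σ√2. Roughly, its statistic is the paired one multiplied by √(1−ρ), so the paired statistic must exceed 1.96/√(1−ρ). That threshold is 2.34, 2.77, 3.58 and 4.38 at ρ = 0.3, 0.5, 0.7 and 0.8, against an expected value of about 2.71.

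**3. Simulation inside the rank branch** (normal scores, 20,000 trials per setting; drug shift = 0.7σ√(2(1−ρ))):

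| ρ | Shift (σ) | Mann-Whitney power | Signed-rank power | Mann-Whitney rejection under the null |
|---|---|---|---|---|
| 0 | 0.99 | 0.71 | 0.69 | 4.7% |
| 0.3 | 0.83 | 0.56 | 0.69 | 2.0% |
| 0.5 | 0.70 | 0.40-0.41 | 0.69 | 0.8% |
| 0.7 | 0.54 | 0.18 | 0.69 | 0.1% |
| 0.8 | 0.44 | 0.07-0.08 | 0.69 | <0.1% |

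If a significant Kruskal-Wallis test is required first, Mann-Whitney power falls to 0.66, 0.48, 0.31, 0.10 and 0.03. For the three-condition tests themselves (3,000 trials), Kruskal-Wallis has 0.75, 0.38, 0.13 and 0.05 at ρ = 0, 0.5, 0.7 and 0.8; Friedman has about 0.60-0.62 throughout.

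**4. Primary scale under the whole two-branch rule.** Scores were simulated as 0-10 integers centred at 6 with SD 1.5-2.5 (assumed). Shapiro-Wilk at 5% was applied to the differences, to the pooled values, or to each condition, since the plan does not say which. There was no Kruskal-Wallis gate. Normality is rejected in 8-81% of trials.

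| ρ | Overall power, plan | Overall power, signed-rank in the rank branch |
|---|---|---|
| 0.3 | 0.62-0.69 | 0.67-0.70 |
| 0.5 | 0.50-0.67 | 0.65-0.69 |
| 0.7 | 0.32-0.61 | 0.62-0.69 |
| 0.8 | 0.20-0.54 | 0.60-0.66 |

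**5. Five-level ordinal scale**, an assumed stand-in for Ashworth and MRC, with the 0.7 effect on the latent scale and no gate. At ρ = 0.3, 0.5, 0.7 and 0.8, Mann-Whitney has 0.53-0.54, 0.37-0.38, 0.17-0.18 and 0.07-0.08. Signed-rank has 0.61, 0.58-0.59, 0.53-0.55 and 0.48-0.50.

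**6. Other reading of the effect size.** If 0.7 is scaled to the SD of a single score, Mann-Whitney stays near 0.40 (0.39-0.42) at every ρ, while signed-rank is 0.41, 0.55, 0.69 and 0.88 at ρ = 0, 0.3, 0.5 and 0.7.

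**The case against.** The strongest reply is that the effect on the primary outcome is conditional and may be small. It needs normality to be rejected, and the lowest overall figures come from an assumed SD of 1.5 with normality tested on pooled values. At SD 2-2.5 and ρ = 0.5 the plan's overall power is 0.60-0.66, against 0.68-0.70 for the paired t-test; at ρ = 0.3 it is 0.66-0.69 against 0.70. The only unconditional use is on secondary outcomes, and there the Mann-Whitney step is qualified. All of this stands, and it limits what can be said about size. It does not make an independent-groups test suitable for paired data.

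It can also be said that the steep fall with ρ depends on fixing the paired effect at 0.7, which shrinks the raw shift as ρ rises. That is so, but under the other reading a gap remains and still widens with ρ.

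A third point cuts the other way. The tests are conservative only with one value per person per condition. If an analyst pooled the three weekly scores of each period as though independent (45 against 45), null rejection was about 7-14% in three of four assumed correlation settings and about 1% in the fourth. The plan does not say it will pool, so this is a possibility only; if it happened, the harm would be greater.

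Finally, the normal branch is not fully specified either: it says ANOVA without saying repeated measures. Its follow-up test, however, is clearly paired.

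**Conclusion.** The concern holds and must be fixed before analysis. The rank branch does not match the crossover design, the normal branch or the sample-size basis. Inside that branch, power falls from about 0.69 with the signed-rank test to about 0.40 at ρ = 0.5 and 0.18 at ρ = 0.7. There is no material loss near ρ = 0, but a design that uses patients as their own controls presumes meaningful correlation. For the primary outcome the overall loss is smaller, ranging from slight to large according to ρ, SD and how normality is tested, none of which the documents give. For Ashworth and MRC the mismatch applies every time, at least at the Kruskal-Wallis step. With one value per condition and positive correlation, a positive result would not be undermined; a negative one would be hard to interpret.

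**What to change.** In the Statistical analysis section, for the non-normal branch of the spasticity, pain and spasm scales and for Ashworth and MRC:

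- Replace Mann-Whitney with the Wilcoxon signed-rank test on each participant's drug-minus-placebo difference, reported with a Hodges-Lehmann estimate and 95% CI.
- If a three-condition test is kept, use Friedman in place of Kruskal-Wallis, and do not make it a gate for drug versus placebo.
- State the single value per person per condition that enters each test.
- If a period effect is to be allowed for, pre-specify instead the rank-sum test of within-person period differences between the two sequence groups.

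The choice between signed-rank and the period-adjusted test is a real trade-off. In simulation at ρ = 0.5 with an 8/7 split, signed-rank has 0.68-0.69 and the period-adjusted test 0.64 with no period effect. They are about equal (0.63 and 0.64) at a period shift of 0.5 SD of the differences, and at 1 SD the figures are 0.43 and 0.64. Signed-rank also gives up about 2 points of power to the paired t-test on normal data, and it drops zero differences (24-46% of pairs in the five-level simulation).

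The cost is a change of wording and one decision on period adjustment before unblinding. It needs no extra patients, visits or data.

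### The stated power of 0.07 cannot be reconciled with an effect size of 0.7 and 15 participants; it is probably a decimal slip for 0.70

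*Combined protocol and SAP*

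**What the plan says.** The sample-size paragraph follows the Statistical analysis paragraph of the Research Plan and precedes Data Management. It sets alpha at 0.05 and continues: "power=0.07, and expected effect size of 0.7, the required sample size is 15 participants". It then explains why 15 is the whole trial and not a per-group figure: "This number is total given this is a paired analysis with the patients serving as controls for themselves".

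The Statistical analysis paragraph describes the tests. For normally distributed data it starts with an ANOVA across baseline and the two treatments, and then: "Further testing for differences between groups will be carried out using the Paired-samples T-test". The alternative reads "If the data is not normal, the non-parametric Kruskal-Wallis one way analysis of variance followed by the" Mann-Whitney U test.

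The protocol does not say whether alpha is one-sided or two-sided, which standard deviation the effect size is divided by, what within-patient correlation is expected, or how many patients may drop out. Power is stated nowhere else.

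**The concern.** A planned power of 0.07 is barely above the type I error rate of 0.05. Taken literally, the trial expects to detect its own anticipated effect 7% of the time, and no one would plan for that. It also conflicts with the numbers beside it, because an effect of 0.7 in 15 paired observations gives far more power than 0.07.

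This is the only power statement in the document. In a trial of 15 patients a null result is a real possibility, and a reader will look here to see how likely the design was to miss an effect of the expected size. The printed figure misleads that reader, and its replacement cannot be settled from the text, because more than one sensible set of inputs leads to 15.

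**Working it through.** **Inputs.** From the sample-size paragraph: alpha 0.05, power 0.07, effect size 0.7, N = 15 in total, paired analysis. From the Statistical analysis paragraph: paired t-test. Assumed, because not stated: d = 0.7 is the mean within-patient difference divided by the SD of the differences, and all patients complete both periods. Both one-sided and two-sided alpha are tried.

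**Formula.** For n pairs the test statistic has a noncentral t distribution with n − 1 degrees of freedom and noncentrality 0.7√n. Power is the probability that it falls beyond the critical value of the central t distribution.

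**Step 1: try to reproduce 15 from the printed inputs.** At n = 2 the noncentrality is 0.7 × √2 = 0.990 on 1 degree of freedom. Power is 0.073 two-sided and 0.134 one-sided, so 2 patients already meet a target of 0.07. The normal approximation, n = ((z for alpha + z for power)/d)², gives ((1.960 − 1.476)/0.7)² = 0.478 two-sided, which rounds up to 1. The stated 15 is not reproduced.

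**Step 2: the power that 15 patients give.** The noncentrality is 0.7 × √15 = 2.711 on 14 degrees of freedom.

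| n | Two-sided 0.05 | One-sided 0.05 |
|---|---|---|
| 2 | 0.073 | 0.134 |
| 14 | 0.678 | 0.798 |
| 15 | 0.713 | 0.824 |
| 18 | 0.799 | 0.886 |
| 19 | 0.823 | 0.901 |

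Using n − 2 degrees of freedom, as in a two-period crossover analysis, changes the two-sided figure at n = 15 only to 0.708. For power to be 0.07 at n = 15, the effect would have to be about 0.115.

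**Step 3: which target returns 15?**

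- Power 0.70, two-sided: smallest n is 15.
- Power 0.80, one-sided: smallest n is also 15.
- Power 0.80, two-sided: smallest n is 19.
- Power 0.70, one-sided: smallest n is 12.
- 0.07 read as the type II error, so power 0.93: 27 two-sided or 22 one-sided.

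The first line needs only a moved decimal point, so it is the simplest explanation. The second fits equally well numerically.

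**Step 4: how much depends on the standardisation.** If 0.7 is a difference divided by the between-patient SD, the effect on the differences is 0.7/√(2(1 − ρ)), where ρ is the within-patient correlation. The document gives no ρ, so these values are assumed:

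| ρ | Effect on differences | Two-sided power, n = 15 |
|---|---|---|
| 0 | 0.495 | 0.43 |
| 0.3 | 0.592 | 0.57 |
| 0.5 | 0.700 | 0.71 |
| 0.7 | 0.904 | 0.90 |

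**Step 5: does the figure carry over to the fallback test?** The Mann-Whitney test ignores the pairing on which the total of 15 rests. Simulation used 15 pairs, normal data, a difference of 0.7 SD of the differences, two-sided 0.05 and 20,000 trials per setting. The Mann-Whitney test had power of about 0.56, 0.40 and 0.18 at assumed correlations of 0.3, 0.5 and 0.7, against about 0.71 for the paired t-test on the same data. At zero correlation the Mann-Whitney figure is also about 0.71. The paired figure therefore applies to the fallback only if a patient's two measurements are uncorrelated.

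**The case against.** The strongest reply is that this is a one-digit typographical error, that few readers would believe a planned power of 7%, and that a completed trial's null result is read mainly from the estimate and its confidence interval. That is fair, and it limits the weight of the point: nothing here shows that the design was weakened by the misprint. It does not remove the need for a correction, because silently reading 0.70 would be a guess between two readings that both give exactly 15.

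A second objection is that one cannot call the intended power unrecoverable and also say that 15 may stand. If the sponsor meant 0.80 two-sided, 15 is too few and 19 would be needed. This stands as a caution. It does not undo the correction, because a sentence stating the power that 15 completers provide is true whatever was intended.

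A third is that the plan runs an ANOVA over three conditions before the t-test. If the t-test were run only after a significant ANOVA, power would be lower: about 0.66 instead of 0.71 in one simulated scenario (15 patients, correlation 0.5, baseline mean equal to placebo mean). The plan states no such gating rule, so this is a possible qualification and not a correction to the 0.713.

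Finally, choosing an unpaired test for crossover data is a separate question from the misprint. It matters here only because a corrected power sentence must say which test it describes.

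**Conclusion.** The concern holds. With alpha 0.05 and effect size 0.7, a power of 0.07 corresponds to 2 patients, not 15, and no variant tried returns 15 from the printed inputs. This is certain and does not depend on sidedness.

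That 0.07 stands for 0.70 is probable but inferred. If 0.7 is standardised by the SD of the differences and all 15 patients complete, power is 0.713 two-sided or 0.824 one-sided. The chance of missing a true effect of 0.7 is then 1 − 0.713 = 0.287, about 29%, or 1 − 0.824 = 0.176, about 18%. If 0.7 uses the between-patient SD, two-sided power runs from 0.43 to 0.90 over the assumed correlations of 0 to 0.7.

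This should be fixed: the only power statement is wrong as printed, but the error does not itself harm the trial.

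**What to change.** The sponsor should confirm three things: the intended power, whether alpha 0.05 is one-sided or two-sided, and how the effect size of 0.7 is standardised. The sentence should then be replaced.

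- If two-sided: *With 15 patients completing both periods, a paired t-test of drug against placebo at two-sided alpha 0.05 has power of about 0.71 for an effect size of 0.7, defined as the mean within-patient difference divided by the SD of the differences.*
- If one-sided: the same sentence with *one-sided* and *about 0.82*.
- If 0.7 uses the between-patient SD: state the assumed within-patient correlation as well, and the power it gives.

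In each case, add that the figure applies to the paired t-test and not to the non-parametric fallback. If the t-test is meant to be conditional on the ANOVA, say so, because the figure would then be somewhat lower.

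The cost is one sentence after three confirmations. Enrolment, conduct and analysis do not change when the power for 15 patients is restated. Should the sponsor confirm that 0.80 two-sided was intended, it must decide whether to accept the power that 15 patients provide or to revisit the number.
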